### 7.3 Assessment of secondary endpoint/outcome(s)

The following secondary endpoint variables will be obtained and noted on bedside paper case report forms at the scheduled time points of assessment and blood sampling:

- Discharge date from ICU as determined by the moment of decision made by treating physicians for discharge, even though immediate discharge may not be possible due to capacity reasons of the targeted peripheral ward.
- Respiratory support.
- Vasoactive Drugs.
- Serious (Adverse) Events/Death.

### 7.4 Assessment of other study variables

The following further study variables will be obtained and noted on bedside paper case report forms:

- Weight
- Sex
- Age in years and months. If neonatal ( $<28\text{ d}$ ): postnatal days + postconceptional age
- Other drugs, exogenous vasopressin administration

### 7.5 Assessment of safety and reporting

#### 7.5.1 Definition of Serious Events (SEs)

A **serious event** is any unfavourable event for which a causal relationship to sampling of biological material or the collection of health related personal data cannot be ruled out, and which:

- requires hospitalisation or prolongation of an inpatients' hospitalisation,
- results in persistent or significant disability or incapacity, or
- is life-threatening or results in death,

If a serious event occurs the research project will be set on hold.

### 7.5.2 Assessment and Documentation of SEs

The assessment by the project leader with regard to the project-specific measure relation is done according to the following definitions:

- Unrelated: The occurrence of the event has no temporal relationship to the project-specific measures applied and can be explained by the underlying disease or other factors.
- Related: There is a plausible temporal relationship between the occurrence of the event and the project-specific, applied measures and cannot be explained by the underlying disease or other factors.

All SEs are to be documented in the participants' file and on the SE report form. A sample form is appended to the Protocol and can be downloaded at [www.swissethics.com](http://www.swissethics.com).

### 7.5.3 Reporting of SEs, Safety and Protective Measures

The project leader shall report any occurring SE to the responsible EC within 7 days (and to the FOPH in case of involved radioactive sources). He/she shall also submit a report which evaluates the relationship between the event reported and the methods of collecting health related personal data or sampling of biological material within that project, furthermore proposals how to proceed with the project.

The project leader will notify the EC within 7 days of any immediate other safety and protective measures, which have to be taken during the conduct of the research project. In addition, the project leader will explain the circumstances, which necessitated the safety and protective measures.

## 8. STATISTICAL METHODOLOGY

### 8.1 Determination of Sample Size

The sample size calculation is based on the primary objective, namely to investigate the average change of blood copeptin levels (mean difference between time-points, i.e. from admission to 12h, from 12h to 24h, from 24h to 48h) in critically ill children and neonates with both arterial normo- and hypotension over 48h after ICU admission.

#### Assumptions:

1. We hypothesize that the mean difference in blood copeptin levels between two time-points is *not* 0 (as assessed by a two-sided t-test, assuming equal variance).
2. We base corresponding sample size calculations on the data in the study from Lee et al. (2013) since this paper provides blood copeptin levels at different time points from patients with septic shock admitted to the PICU, i.e. a population similar to a part of the population expected in the present study:

Table 2: Blood copeptin levels measured in the study of Lee et al. (2013).

Time	Healthy n=70	Sepsis n=53	Septic shock (PICU), n=13	Difference in means between period	Interquartile range (IQR)
	Median (IQR) [ng/mL Copeptin]	Median (IQR) [ng/mL Copeptin]	Median* (IQR) [ng/mL Copeptin]		
0-24 h	12 (0.8-1.8)	1.5 (1.0-2.2)	0.9 (0.8-1.2)	-	0.4
48 h			1.2 (0.7-1.8)	0.3	1.1
72 h			1.25 (0.8-1.8)	0.05	1.0
96 h			1.5 (1.3-1.7)	0.25	0.4
120 h			2.0 (1.0-2.2)	0.5	1.2

\*we assume normal distribution and use the reported median as mean in the following, as discussed below.

3. For the relevant time points the maximum mean difference between time points is  $d = 0.3 \text{ ng/mL}$  (from 0-24h to 48h, highlighted in blue in the Table 2 above), the interquartile range (IQR) is approximately 1.1 ng/mL.
4. We assume normality, which seems reasonable given the data only seem slightly skewed (median - 0.5, median +0.6). The IQR is then approximately 4/3 of a standard deviation (sd), i.e.  $sd = 0.75 \times 1.1 \text{ ng/mL} = 0.82 \text{ ng/mL}$ .

5. For the power calculation, we fix the significance level at 5%, and vary the power to determine the effect on possible sample size (Table 3). We use the standard difference in means calculation (t-test).

Table 3: Power calculation without adjustment for drop-out or other reasons of missing data.  $^{*}\text{effect} = d/\text{sd}$

Power	Sample size for effect* = 0.36 (0.5)
0.8	62 (26)
0.9	82 (37)
0.95	101 (45)

6. The median PICU length of stay was 6 days, whereas internal data of Zurich's PICU suggests an even shorter median length of stay (1.3 days, see below), with only 40% of patients staying at least 48h. We thus assume a 60% drop out before the end of the targeted observation period of 48 hours (see above), which means that we need to multiply our sample size by 10/4.

7. We assume that at least 90% of the blood copeptin values are within the measurable range of the assay (0.02-4.8 ng/mL), which means that we need to multiply our sample size by 10/9 to account for an additional potential 10% of missing data.

**Conclusion:** Assuming 80% power, 5% significance level a **sample size of 62 x 2.5 x 1.1 = 170 patients** with an effect size of 0.36 (**mean difference d=0.3 ng/mL**,  $\text{sd}=0.8 \text{ ng/mL}$ , 60% drop out, 10% of data below lower limit of quantification) is needed for this study.

## 8.2 Planned analysis

### 8.2.1 Datasets to be analysed

#### Analysis population

- The primary analysis population for the assessment of the mean difference in blood copeptin levels between time points within the first 48 hours after ICU admission is the full analysis set of all included patients (intention-to-treat analysis). Associations of copeptin levels with the following covariates will be analysed in all included patients: arterial blood pressure, severity of disease and age. Associations with further patient characteristics as septic shock, heart failure, traumatic brain injury, perinatal asphyxia will be analysed in affected patients only.
- The secondary analyses (association of copeptin levels with clinical outcome) will be done in all patients for whom the respective information is available (see 8.2.2 Handling of Missing data).

#### Analysis tool

All relevant clinical and laboratory parameters obtained during the study period will be analysed using SPSS 22 (IBM, Armonk, NY, USA), R (R Core Team, Vienna, Austria), and NONMEM (Icon Development Solutions, [name], USA).

#### **Secondary endpoints**

Finally, measured blood copeptin levels and/or model-derived individual parameters characterizing the course of individual blood copeptin levels will be investigated as predictor variables for length of ICU stay, length of respiratory support and survival in a time-to-event analysis, and for severity of disease (including dose of catecholamine therapy) in a regression analysis.

In a more advanced analysis, also the time-course of blood pressure measurements will be analysed and characterized in a mixed-effect regression analysis. The temporal and dynamic relationship between blood copeptin and blood pressure will be furthermore assessed.

### **8.2.2 Handling of missing data**

#### **Primary outcome:**

Missing blood copeptin and/or blood pressure data is expected to occur at time points after baseline assessment because of the following reasons:

- Transfer to another unit (mainly associated with improvement of patient condition)
- Death (associated with worsening of patient condition)

Missing copeptin and/or blood pressure data may occur at any time point because of the following reasons:

- Measurement below the limit of quantification of the analytical method (only copeptin)
- Technical difficulties in blood sampling and/or blood pressure measurement
- Consent withdrawal

The remaining covariates, including age and medical condition (including septic shock, heart failure, traumatic head injury, brain tumor and/or intracranial operation, perinatal asphyxia and severity of disease) are unlikely to be missing since they are assessed at ICU admission and included in the electronic patient record.

For the initial assessment of blood copeptin kinetics, all individual data independent of later missing blood copeptin measurements will be included in the analysis (“full analysis”, i.e. according to the intention-to-treat principle). One advantage of the planned mixed-effect modelling is that it can indeed handle unbalanced individual data. Measurements below the limit of quantification will not be omitted but included as censored measurements. Missing covariates at specific time points (age, blood pressure) will be imputed or interpolated based on other observed individual data (e.g. based on previous and/or subsequent assessments).

In a sensitivity analysis, the time-course of only complete patient data over 7 days (“complete case analysis”, i.e. per protocol) will be compared with the “full analysis set” and model parameters will be assessed for a bias induced by potentially copeptin-dependent (i.e. non-random) missingness reasons.

If a bias is suggested we will furthermore investigate the time-course of copeptin in patients with missing data, stratified for different reasons of missingness (“stratified sub-analyses”).

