This study may include patients, who themselves or whose caretakers may not be able to give written informed consent in emergency situations. This may be due to acute clinical deterioration, resuscitation and/or sedation of the patients. Further, care takers may not be present or accountable for formal medical explanations and may not be able to give informed consent at the time of intensive care unit admission due to the deterioration of their child. In this case, blood samples for copeptin will be taken, but not analyzed. As soon as possible, but latest 24 hours following intensive care unit admission, written informed consent will be obtained from care takers, if patient  $< 14$  years or if patient  $\geq 14$  years and sedated for more than 24 hours. If the adolescent ( $\geq 14$  years of age) stays sedated or unable to give informed consent for more than 24 hours, the presumptive will of the adolescent has to be taken into account by the legal care takers when giving informed consent in her/his place. Written informed consent will be obtained from the patient her-/himself, if  $\geq 14$  years and sedated for less than 24 hours in agreement with HFG Art. 30, Abs. 2. If a legal care taker gives informed consent in place of an adolescent ( $\geq 14$  years of age), the informed consent must be obtained from the adolescent her-/himself as soon as the adolescent is able to give consent her-/himself. If the adolescent is not willed to give consent, all data and blood products obtained until then will be destroyed in this case. The volume of blood necessary for the copeptin analysis (600  $\mu$ l each sample) is not relevant for any age group including neonates. The additional clinical data needed for primary and secondary endpoint assessment is open-label. Study relevant data is available in medical files and electronic patient data management systems of the intensive care ward anyway. In addition, copeptin analyses will be performed only for blood samples from patients with written informed consent using a pooled batch of blood samples several weeks later.

In case written informed consent cannot be obtained within 24 hours after admission, the patient will not be included in the study, all blood samples will be destroyed and no patient data will be analyzed (in agreement with HFG Art. 31 Abs.1+2).

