### **3.3 Risk-Benefit Assessment**

The study period will cover up to 168 hours in which a maximum of 6 blood samples (minimum 600 µl each) from peripheral venous lines or central venous and arterial catheters will be analysed for baseline copeptin distribution. The required amounts of blood volume for analyses are clinically not relevant for any age group. As critically ill patients frequently require invasive arterial blood pressure monitoring and central venous access for fluid and medicament administration, the required catheters for blood withdrawal are generally in place. Importantly, each study blood withdrawal will be grouped together with otherwise medically indicated blood withdrawals, causing no additional catheter manipulation, pain or harm for the patient. The comparison of blood copeptin and arterial hypotension will define the primary endpoint.

All further laboratory parameters proposed in “Schedule of Assessments (Flow of Research Project)” are considered to be secondary endpoints. Analyses of these laboratory values will only be included in the study, if their sampling is indicated for any other medical reason.

Children and neonates included in this study do not directly benefit from the study. However, the recruited patients help to identify future patient cohorts, which could benefit from individualized vasopressin administration supporting and replacing at least a part of the current standard fluid and catecholamine therapy in hypotension and shock. Moreover, the potential association between copeptin levels and outcome might provide new insights when it comes to counselling parents experiencing an emotionally challenging period of their lives.

Security of the collected data is given through data collection in especially signed folders (including case report forms) in the intensive care ward and through data storage in an especially signed electronic file (University Children’s Hospital Zurich). Data in the folders on the ward contain only data stored in clinical patient files anyway. Data will be managed strictly confidential, after initial data acquisition data will be coded through electronic storage with a study number and age (years + months, if <28 d in days); access to original data will only be given to the study personal and to institutions mentioned above. There will be no transfer of non-coded data to other storage systems outside the University Children’s Hospital Zurich.

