## **4. OBJECTIVES, ENPOINTS/OUTCOMES AND OTHER STUDY VARIABLES**

### **4.1 Objectives**

#### **Primary objective**

The primary objective is to investigate the average change of blood copeptin levels in critically ill children and neonates with both arterial normo- and hypotension over 48h after intensive care unit (ICU) admission, and in a second step to describe the natural course and variability of copeptin levels over a period of up to 7 days after ICU admission. In this scope we will also investigate the association of patient characteristics (covariates) with blood copeptin baseline levels at ICU admission and the course of blood copeptin levels during ICU stay. In particular the association with the following factors will be investigated:

- Arterial blood pressure (in particular hypotension vs. normotension), to identify patients that may most benefit from exogenous AVP treatment
- Septic shock
- Heart failure
- Traumatic head injury, brain tumor and/or intracranial operation
- Perinatal asphyxia
- Severity of disease (disease score)
- Age

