#### Arterial blood pressure and hypotension

Hypotension is defined as systolic arterial pressure below age specific 5th percentiles according to reference values established in the context of the last International Pediatric Sepsis Consensus Conference (published 2005): newborn 0 days to 1 week 59 mmHg, neonate 1 week to 1 month 79 mmHg, infant 1 month to 1 year 75 mmHg, toddlers and preschool children 1 to 5 years 74 mmHg, school age children 5 to 12 years 83 mmHg, adolescent and young adult 12 to 18 years 90 mmHg. Blood pressure will be measured invasively via indwelling central or peripheral arterial catheters or non-invasively via auscultatory or oscillometric techniques.

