On admission demographic baseline data will be recorded on paper bedside case report forms as outlined in "Schedule of assessment (Flow of research project)" (i.e. age (years + months; if <28 days: postnatal days and postconceptional age), Apgar-score, arterial umbilical cord pH; diagnosis; disease-severity-scores; operation, preoperative parameters; weight; sex). Blood samples (600 µl) will be taken from all study patients on specific points of time (on admission, with 12, 24, 48, and, if still in ICU with 96, and 168 hours following admission), processed and stored at -80 °C for batch analyses later. Just before or after blood sampling the following clinical data will be recorded: arterial blood pressure; vital parameters (respiratory rate, peripheral oxygen saturation, arterial oxygen saturation, perfusion index, heart rate, peripheral pulses, capillary refill, urine output); laboratory values (sodium, potassium, calcium, chloride, troponin, creatine kinase, creatine kinase MB, pH, partial arterial oxygen pressure (PaO2), partial carbon arterial carbon dioxide pressure (PaCO2), base deficit, arterial lactate, glucose, alanine transaminase (ALT), creatinine, C-reactive protein, haemoglobin, white blood cell count, total bilirubin); neurological parameters (Glasgow Coma Scale, CT-findings (abnormal cisterns, midline shift >5mm, traumatic subarachnoidal haemorrhage, seizures, intracranial and cerebral perfusion pressure (if invasively monitored)); neonatal parameters (results of neonatal neurological imaging (cranial ultrasound and/or MRI) and performance of neonatal cooling as prevention of neurological damage). Importantly, laboratory parameters will only be assessed, if their analysis is otherwise medically indicated for limitation of blood loss and phlebotomy. As most critically ill patients have to be equipped with invasive hemodynamic monitoring allowing repetitive blood withdrawal, no additional phlebotomy should be necessary. Copeptin values will only be analysed, when the study blood sample can be taken alongside with other medically indicated blood samples.

If the study patient is discharged from the ICU, the study period ends and no further blood samples or clinical data will be taken or analysed. Length of ICU stay will be noted. Every patient will be followed by study investigators for a total of 28 days to note date of discharge from ICU, Hospital and date of death, if applicable.

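### Section 8.2.2 lets a missing blood pressure be filled from assessments 12 to 72 h away, with no prior look-up in the patient record; if done by interpolation, this misclassifies hypotension at the filled points

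*Protocol*

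**What the plan says.** All references are to the protocol.

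- **The rule.** Section 8.2.2 (Primary outcome) states: "Missing covariates at specific time points (age, blood pressure) will be imputed or interpolated based on other observed individual data". The example in brackets is "e.g. based on previous and/or subsequent assessments".
- **The schedule.** Section 5.2 sets samples "on admission, with 12, 24, 48, and, if still in ICU with 96, and 168 hours following admission". Pressure is recorded at the same moments: "Just before or after blood sampling the following clinical data will be recorded: arterial blood pressure".
- **The role of blood pressure.** Section 4.1 lists it first among the factors to be related to copeptin: "Arterial blood pressure (in particular hypotension vs. normotension), to identify patients that may most benefit from exogenous AVP treatment". Section 3.3 goes further: "The comparison of blood copeptin and arterial hypotension will define the primary endpoint". Section 8.2.1 puts blood pressure into the copeptin kinetic model as a covariate.
- **The classification.** Section 4.2 uses a lower-tail cut-off: "Hypotension is defined as systolic arterial pressure below age specific" 5th percentiles.
- **The record.** Section 2.4 says: "Study relevant data is available in medical files and electronic patient data management systems of the intensive care ward anyway". Section 5.4 says clinical parameters are available in the medical charts. Section 7.2 lists arterial blood pressure among the items on the bedside case report forms, and section 9.4 says those forms hold only information from the medical file.

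Section 8.2.2 relies on the electronic record for the remaining covariates and for catecholamine doses. It does not mention the record for a missing blood pressure.

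**The concern.** Hypotension is an event in the lower tail of a quantity that can change within hours in intensive care. Within one age band, linear interpolation between two normotensive readings cannot give a hypotensive value, so a short episode between two assessments disappears. Conversely, one very low neighbour can pull a normotensive point below the cut-off. The errors run in both directions, with a net loss of hypotensive points.

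What is at stake is the contrast between hypotension and normotension, the covariate of chief interest. Using subsequent assessments also lets a later pressure stand as a predictor of an earlier copeptin value. That is awkward in a study that wants to describe the temporal relation between the two (sections 4.1 and 8.2.1).

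**Working it through.** **Step 1. Distance to the neighbouring assessments.** The times are 0, 12, 24, 48, 96 and 168 h, so the gaps are 12, 12, 24, 48 and 72 h. Admission has only a later neighbour (12 h), and 168 h has only an earlier one (72 h before).

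**Step 2. Misclassification at an interpolated point.** The protocol gives no figure to reproduce here, so the inputs are assumptions: standardised Gaussian systolic pressure; true hypotension prevalence p = 15% or 25%; correlation ρ = 0.3, 0.5 or 0.7 between adjacent readings and ρ² between the two outer ones; the missing middle value replaced by the mean M of its neighbours.

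- Cut-off: c = Φ⁻¹(p).
- Variance of M: v = (1 + ρ²)/2.
- Correlation of M with the true value X: ρ/√v.
- Share flagged hypotensive: q = Φ(c/√v).
- Truly hypotensive and flagged: j = P(X < c and M < c), from the bivariate normal.
- Share of truly hypotensive points recovered = j/p. Share of flags that are false = 1 − j/q.

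Example with p = 0.15 and ρ = 0.5: c = −1.036, v = 0.625, c/√v = −1.311, q = 0.095, j = 0.0513. Recovered: 0.0513/0.15 = 34%. False flags: 1 − 0.0513/0.095 = 46%.

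| p | ρ | Recovered | False among flagged | Apparent prevalence |
|---|---|---|---|---|
| 15% | 0.3 | 20% | 62% | 8% |
| 15% | 0.5 | 34% | 46% | 9.5% |
| 15% | 0.7 | 52% | 32% | 12% |
| 25% | 0.3 | 34% | 54% | 18% |
| 25% | 0.5 | 47% | 40% | 20% |
| 25% | 0.7 | 63% | 28% | 22% |

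**Step 3. Other assumptions.** A separate simulation used the actual visit gaps, prevalence 10–30%, a between-patient variance share of 0.3 or 0.5, and within-patient correlation decaying with a time constant of 6–48 h. Interpolation recovered 16–82% of truly hypotensive points and lowered the apparent prevalence in every scenario (for example from 20% to 15.0–18.8%). Carrying one neighbouring value across, under the Step 2 assumptions, leaves prevalence unchanged but recovers only 28–60%.

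**Step 4. Effect on the hypotension contrast.** Suppose a share f of points is filled at random and mean copeptin depends only on true hypotension status. Then P = (1 − f)p + fq is the share classed hypotensive, and the observed contrast as a fraction of the true one is

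[(1 − f)p + fj]/P − f(p − j)/(1 − P).

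Example with p = 0.15, ρ = 0.5, f = 0.10: P = 0.135 + 0.0095 = 0.1445. First term: (0.135 + 0.0051)/0.1445 = 0.970. Second term: 0.10 × 0.0987/0.8555 = 0.012. The contrast is 0.958 of its true size, a loss of about 4%.

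| Share filled (assumed) | Shrinkage over all six settings |
|---|---|
| 2% | about 1% |
| 5% | 2–3% |
| 10% | 3–6% |
| 20% | 7–13% |

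**Step 5. The primary test.** Sections 8.1 and 8.2.1 size and analyse the study by a t-test on copeptin change between time points. Blood pressure does not enter it.

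**The case against.** The other side has several good points.

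- **The method is not fixed.** The text allows imputation or interpolation, with neighbouring assessments as an example. A reader might infer that interpolation is mandated, or that filled values will be treated as observed with standard errors that are too small. The protocol states neither, and multiple imputation is already permitted. What stands is that the wording explicitly allows the unsuitable method.
- **Section 2.4 is general.** A reader might infer that it places the pressure at the sampling time in the electronic system, so that the rule contradicts the protocol. That sentence belongs to the consent section and names neither blood pressure nor sampling time. Only together with sections 5.4, 7.2 and 9.4 does it indicate that charted pressures are in the record.
- **The record cannot help in every case.** After transfer or death there is no study sample and so no pair to misclassify. Where measurement failed, the chart may be empty too. The point concerns samples taken in the unit with no pressure on the form. Since pressure is to be recorded beside each sample, these are probably few.
- **A sensitivity analysis is planned.** Section 8.2.2 compares complete cases over 7 days with the full set. Complete data would contain no filled pressures, but the synopsis says only 13% of patients stay beyond 7 days. That comparison uses a small, sicker group and does not isolate the filling of blood pressure.
- **Dropping pairs has a cost.** Leaving the pair missing would discard observed copeptin values and might select against patients whose pressure was hard to measure. This is accepted, and the fix does not rely on it.

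**Conclusion.** The point holds in a limited form. Section 8.2.2 permits missing pressures to be filled from assessments 12–72 h away and does not first call for the charted value. If interpolation is used, about 20–63% of truly hypotensive filled points are recovered, under the assumed prevalence of 15–25% and adjacent correlation of 0.3–0.7, and the hypotension–copeptin association is attenuated. These percentages apply to filled points only. At study level the loss would be about 1% of the contrast if 2% of points are filled and 7–13% if 20% are. Those shares are assumptions, because the protocol gives none, and the true share is probably small.

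A reader might go further and conclude that the primary result is biased, or that every error moves points to normotension. Neither is supported: the primary t-test does not use blood pressure, and 28–62% of the points that interpolation flags are false positives. The change is still worth making, because it concerns the main covariate and a better source probably exists for at least some of the affected samples.

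**What to change.** Replace the sentence in section 8.2.2, as far as it concerns blood pressure, with:

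> A blood pressure missing from the case report form at a copeptin sample is first taken from the patient record, using the charted value closest to the recorded sampling time. Only if none exists is it multiply imputed; it is not filled by interpolating between scheduled assessments. The blood pressure association is repeated using observed pressures only.

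The cost is a record look-up for the affected samples and slightly more analysis work. Sample size, sampling schedule and patient procedures do not change.
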